5.2. Exclusion Criteria

Participants are excluded from the study if any of the following criteria apply:

Medical conditions

11. Have T1D.
12. Have a history of chronic or acute pancreatitis any time prior to screening.
13. Have a history of or diagnosis during screening-dilated fundoscopic examination of
 - proliferative diabetic retinopathy, or
 - diabetic maculopathy, or
 - nonproliferative diabetic retinopathy that requires acute treatment.
14. Have any of these CV conditions within 60 days prior to screening:
 - acute myocardial infarction,
 - cerebrovascular accident (stroke), or
 - hospitalization due to CHF.
15. Have NYHA Functional Classification Class IV CHF.
16. Have a history of ketoacidosis or hyperosmolar state/coma.
17. Have a history of severe hypoglycemia and/or hypoglycemia unawareness within the 6 months prior to Visit 1.
18. Have a known clinically significant gastric emptying abnormality (for example, severe diabetic gastroparesis or gastric outlet obstruction), have undergone or plan to have during the course of the study: gastric bypass (bariatric) surgery or restrictive bariatric surgery (for example, Lap-Band®), or chronically take drugs that directly affect GI motility.
19. Have acute or chronic hepatitis, signs and symptoms of any liver disease other than NAFLD, or ALT level >3.0 times the ULN for the reference range, as determined by the central laboratory at study entry. Participants with NAFLD are eligible to participate in this study if their ALT level is ≤ 3.0 times the ULN for the reference range.
20. Have an eGFR ≤ 30 mL/min/1.73 m², calculated by CKD-EPI as determined by central laboratory at screening.
21. Have evidence of a significant, uncontrolled endocrine abnormality (for example, thyrotoxic or adrenal crises), in the opinion of the investigator.
22. Have family or personal history of MTC or MEN 2.
23. Have a serum calcitonin level ≥ 35 ng/L, as determined by central laboratory at V1.

24. Have known or suspected hypersensitivity to study product(s) or related products.
25. Have evidence of a significant, active autoimmune abnormality, for example, lupus or rheumatoid arthritis, that, in the opinion of the investigator, is likely to require concurrent treatment with systemic glucocorticoids during the study.
26. Have had a transplanted organ (corneal transplants [keratoplasty] allowed) or awaiting an organ transplant.
27. Have a history of an active or untreated malignancy or are in remission from a clinically significant malignancy for less than 5 years.

Exceptions:

- a. basal or squamous cell skin cancer
- b. *in situ* carcinomas of the cervix, and
- c. *in situ* or Grade 1 (for example, Gleason 6 or lower) prostate cancer.

28. Have a history of any other condition such as known drug or alcohol abuse, or psychiatric disorder that, in the opinion of the investigator, may preclude the participant from following and completing the protocol.
29. Have any chronic hematological condition that may interfere with HbA1c measurement such as hemolytic anemias and sickle cell disease.
30. Female participants who are pregnant or breast feeding or intending to become pregnant during the course of the study.
31. Have a history of an underlying disease, presence of an underlying disease such as active SARS-CoV-2 infection, or surgical, physical, or medical condition that, in the opinion of the investigator, would potentially affect participant safety within the study or interfere with the interpretation of data.

Prior/concomitant therapy

32. Have been treated with insulin prior to screening.
Exception: use of insulin for gestational diabetes or short-term use (<14 days) for acute conditions, such as acute illness, hospitalization, or elective surgery.
33. Have a history of reduction of dose of dulaglutide weekly, due to intolerance, without successful reescalation, any time prior to Visit 1.
34. Have within 90 days prior to screening received treatment with medications intended to promote weight loss. This includes prescribed or over-the-counter or alternative remedies. See Section 6.8.3 for list of prohibited medications.
35. Are receiving chronic (>14 days) systemic glucocorticoid therapy or have received such therapy within 1 month of Visit 1 or between Visits 1 and 3.
Exceptions: topical, intraocular, intranasal, or inhaled preparations.

Prior/concurrent clinical study experience

36. Are currently enrolled in any other clinical study involving an investigational product or any other type of medical research judged not to be scientifically or medically compatible with this study.

37. Have participated, within the last 30 days, in a clinical study involving an investigational product. If the previous investigational product has a long half-life, 5 half-lives or 30 days (whichever is longer), should have passed prior to screening.
38. Have previously completed or withdrawn from this study or any other study investigating tirzepatide.

Other exclusions

39. Are Lilly employees or are employees of any third party involved in the study who require exclusion of their employees.
40. Are investigator site personnel directly affiliated with this study and/or their immediate families. Immediate family is defined as a spouse, parent, child, or sibling, whether biological or legally adopted.

5.3. Lifestyle Considerations

Diabetes management counseling

Per SoA, Section 1.3, qualified medical staff will provide diabetes management counseling, which will include instructions on diet and exercise and education about the signs, symptoms, and management of hypoglycemia, should it occur.

Participant exercise and diet

Participants should continue their usual exercise habits and generally follow a healthy meal plan, with consistent meal size and time of day, throughout the course of the study.

Participants should not initiate an organized diet and/or exercise (weight reduction) program during the study other than the lifestyle and dietary measures for diabetes treatment.

Dietary counseling will be reviewed throughout the study at every visit, including counseling and management with regard to the weight loss known to be associated with tirzepatide and dulaglutide.

Blood product donation

Study participants should be instructed not to donate blood or blood products during the study.

5.4. Screen Failures

A screen failure occurs when a participant who consents to participate in the clinical study is not subsequently randomly assigned to study intervention. A minimal set of screen failure information is required to ensure transparent reporting of screen failure participants to meet the Consolidated Standards of Reporting Trials publishing requirements and to respond to queries from regulatory authorities. Minimal information includes demography, screen failure details, eligibility criteria, and any SAE.

Individuals who do not meet the criteria for participation in this study (screen failure) may be rescreened at investigator discretion on 1 occasion. Rescreened participants should be assigned a new participant number.

5.5. Criteria for Temporarily Delaying Enrollment of a Participant

This section is not applicable for this study.

6. Study Intervention(s) and Concomitant Therapy

Study intervention is defined as any investigational interventions, marketed products, placebo, or medical devices intended to be administered to/used by a study participant according to the study protocol.

6.1. Study Intervention(s) Administered

Intervention Name	Tirzepatide	Dulaglutide
Dosage Levels	2.5 mg QW 5 mg QW 7.5 mg QW 10 mg QW 12.5 mg QW 15 mg QW	0.75 mg QW 1.5 mg QW 3 mg QW 4.5 mg QW
Route of Administration	SC	
Authorized as defined by EU CTR No 536/2014^a	Not authorized as defined by EU CTR	Authorized as defined by EU CTR and used according to EU Marketing Authorization

Abbreviations: CTR = Clinical Trial Regulation; EU = European Union; QW = weekly.

^a “Authorized investigational medicinal product” means a medicinal product authorized in accordance with Regulation (EC) No 726/2004 or in any Member State concerned in accordance with Directive 2001/83/EC, irrespective of changes to the labeling of the medicinal product, which is used as an investigational medicinal product; “Authorized auxiliary medicinal product” means a medicinal product authorized in accordance with Regulation (EC) No 726/2004, or in any Member State concerned in accordance with Directive 2001/83/EC, irrespective of changes to the labeling of the medicinal product, which is used as an auxiliary medicinal product.

Packaging and labeling

Study interventions will be supplied in accordance with current Good Manufacturing Practice. Study interventions will be labeled as appropriate for country requirements.

6.1.1. Dose Escalation

Tirzepatide dose escalation

Tirzepatide treatment will follow a fixed dose escalation as follows:

- start at 2.5 mg QW. After 4 weeks, increase the dose to 5 mg QW, and
- increase by 2.5 mg every 4 weeks until 15 mg or MTD is achieved.

Dulaglutide dose escalation

Dulaglutide treatment will follow a fixed dose escalation as follows:

- increase to 1.5 mg QW for 4 weeks at randomization, only needed for those starting on 0.75 mg
- increase to 3 mg QW for 4 weeks, and
- increase to and maintain at 4.5 mg QW or MTD for the duration of the study.

Intolerance to dose escalation

If a participant does not tolerate the dose escalation, refer to Section [6.5](#) for additional instructions.

6.1.2. Administration Instructions

Tirzepatide

Tirzepatide is administered QW by SC injection. There are no restrictions on the time of day each weekly dose of study intervention is given, but it is advisable to administer the SC injections on the same day and same time each week, with or without meals.

If a dose is missed, it should be administered as soon as possible within 4 days (96 hours) after the missed dose. If more than 4 days have passed, skip the missed dose and administer the next dose on the regularly scheduled day. In each case, patients can then resume their regular once weekly dosing schedule.

All participants will inject tirzepatide subcutaneously in the stomach area (abdomen) or upper leg (thigh) using the SDPs provided. If the injection is given by someone else, they may inject in the upper arm. A new SDP will be used for each injection. If tirzepatide is to always be injected in the same body region, participants should be advised to use a different injection site each week.

Dulaglutide

Participants in the dulaglutide group will self-administer dulaglutide according to the respective local product labeling.

6.1.3. Medical Devices

Medical devices for tirzepatide and dulaglutide used in this study are manufactured by the sponsor or manufactured for the sponsor by a third party.

Instructions for medical device use for tirzepatide are provided in the Instructions for Use.

Instructions for medical device use of dulaglutide are provided in the respective local product labeling.

All PCs (including malfunction, use error, and inadequate labeling) shall be documented and reported by the investigator throughout the clinical investigation (see Section [8.3](#)) and appropriately managed by the sponsor.

6.1.4. Rescue Therapy

If a participant develops severe, persistent hyperglycemia after randomization, an additional antihyperglycemic medication may be medically indicated after investigator assessment.

Investigators will be trained on the application of criteria for deciding when and how to intervene with participants who do not reach glycemic targets.

First, investigators should confirm participant compliance with the assigned intervention and that they do not have an acute condition causing severe, persistent hyperglycemia.

Conditions for rescue therapy

The criteria for rescue therapy will be based on either FBG or HbA1c as described below.

FBG conditions

This table describes FBG conditions for rescue therapy.

If any of the FBG values exceed the limits outlined below for 2 consecutive weeks and no intercurrent cause of the hyperglycemia can be identified, participants should be treated with rescue medication as an add-on to randomly assigned treatment.

If a participant has persistently elevated FBG defined as...	during this time...	then...
FBG >270 mg/dL (>15.0 mmol/L)	from baseline (V3) to Week 8	participants should be treated with rescue medication as an add-on to randomly assigned treatment.
FBG >240 mg/dL (>13.3 mmol/L)	from Week 9 to Week 16	
FBG >200 mg/dL (>11.1 mmol/L)	Any time after Week 16	

Abbreviation: FBG = fasting blood glucose.

HbA1c conditions

This table describes HbA1c conditions for rescue therapy.

If a participant has an...	during this time...	then...
HbA1c ≥8.5% (≥64 mmol/mol)	any time after Week 24	participants should be treated with rescue medication as an add-on to randomly assigned treatment.

Abbreviation: HbA1c = glycated hemoglobin.

Allowed rescue treatments

The choice of rescue treatment for persistent hyperglycemia will be at the discretion of the investigator. Investigators should follow current published standards of care from the American Diabetes Association and/or the consensus report by the American Diabetes Association and the European Association for the Study of Diabetes (Buse et al. 2020; ADA 2022).

GLP-1 RAs, DPP-4 inhibitors, and pramlintide are not allowed as rescue therapy.

Additionally, tirzepatide is not allowed as rescue therapy for the dulaglutide group.

Rescue therapy will be continued and adjusted per the investigator's discretion.

Rescue therapy may not include modifying the tirzepatide or dulaglutide dose.

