5.1. Inclusion Criteria

Participants are eligible to be included in the study only if all of the following criteria apply:

Age

1. Are 18 years old or of an acceptable age to provide informed consent according to local regulations, whichever is older.

Type of participant and disease characteristics

2. Have been diagnosed with T2D based on the World Health Organization classification or other locally applicable diagnostic standards.
3. Have HbA1c $\geq 7.0\%$ (≥ 53 mmol/mol) to $\leq 9.5\%$ (≤ 80 mmol/mol), as determined by the central laboratory at Visit 1.
4. Are currently on a stable dose of dulaglutide weekly (0.75 mg or 1.5 mg) for at least 6 months prior to Visit 1.
5. No treatment with OAM, or on a stable dose of up to 3 OAMs, which may include metformin, SGLT-2i, and/or sulfonylurea, for at least 3 months before Visit 1.

Weight

6. Have had stable body weight ($\pm 5\%$) during the 90 days preceding screening and agree to not initiate a diet and/or exercise program during the study with the intent of reducing body weight other than the lifestyle and dietary measures for diabetes treatment.
7. Have BMI ≥ 25 kg/m² at Visit 1.

Contraceptive/barrier requirements

8. Contraceptive use by participants should be consistent with local regulations regarding the methods of contraception for those participating in clinical studies.
 - Males may participate in this trial.
Please refer to Section 10.4 for additional guidance related to contraception.
 - WOCBP and women not of childbearing potential may participate in the study.
See Section 10.4 for definitions and additional requirements related to contraception.

Informed consent

9. Capable of giving signed informed consent as described in Section 10.1.3, Appendix 1, which includes compliance with the requirements and restrictions listed in the ICF and in this protocol.

Other inclusions

10. Are reliable and willing to make themselves available for the duration of the study and are willing and able to follow study procedures as required, including, but not limited to
 - self-injecting intervention or injection by a caregiver when applicable
 - willing to be assigned to a different injectable at randomization
 - taking provided study interventions as directed
 - maintaining an eDiary, and
 - completing electronic patient-reported questionnaires.

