6.8.4. Allowed Antihyperglycemic Treatments other than Study Interventions

Antihyperglycemic medications other than study interventions are ONLY allowed during these circumstances:

- for participants who require permanent discontinuation of study intervention but remain in the study
- for rescue therapy after randomization due to severe, persistent hyperglycemia, as described in Section 6.1.4
- during the safety follow-up period or ED visit, and
- short-term insulin use for up to 14 days is allowed for certain clinical situations, for example, elective surgery, during hospitalization, and hyperosmolar states, and must be differentiated from insulin use as rescue therapy when reported in the CRF.

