8.3.3.7. Severe, Persistent Hyperglycemia

Severe, persistent hyperglycemia will be assessed during the study to determine the risk of extreme imbalance in glycemic control.

Investigators will be trained on the application of criteria for deciding when and how to intervene with participants who do not reach glycemic targets. An additional therapeutic intervention should be considered in participants who develop severe, persistent hyperglycemia after randomization. Participants will be treated with rescue medication as an add-on to randomly assigned treatment, and participants will continue to follow the protocol-specified visit schedule as described in Section 6.1.4.

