9.3.6. Subgroup Analyses

Subgroup analyses of the primary endpoint (change from baseline in HbA1c) will be made to assess consistency of the intervention effect across the following subgroups:

- age group: <65 years, ≥65 years
- sex: female, male
- race: white, black, other
- ethnicity: Hispanic, non-Hispanic
- duration of diabetes (≤5 years, >5 to ≤10 years, >10 years)
- baseline HbA1c (≤8.5%, >8.5%), and
- region: NA, EU

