#### **4.6.2.2. Severe Persistent Hyperglycemia**

A summary statistic of initiation of rescue therapy in response to severe, persistent hyperglycemia will be provided by treatment. A listing of participants who initiated rescue therapy will be provided.

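### The only HbA1c rescue criterion pairs 8.5% with 64 mmol/mol, which is about 8.0%, so after Week 24 a participant at 64 to 68 mmol/mol qualifies for rescue in one unit and not in the other

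*Protocol*

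**What the plan says.** Protocol Section 6.1.4 allows rescue on fasting blood glucose (FBG) or on HbA1c. The HbA1c table has one row, "HbA1c ≥8.5% (≥64 mmol/mol", which applies after Week 24 and directs that participants who meet it receive add-on rescue. The FBG table has three limits by study period. The last, after Week 16, is "FBG >200 mg/dL (>11.1 mmol/L".

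The protocol shows its own HbA1c conversion in inclusion criterion 3 (Section 5.1). The lower limit is 7.0% with 53 mmol/mol. The upper limit is 9.5%, given as "≤ 80 mmol/mol), as determined by the central laboratory at Visit 1".

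Other text depends on the Section 6.1.4 criteria:

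- Section 6.8.4 restricts other antihyperglycemic drugs to listed circumstances, one of them "for rescue therapy after randomization due to severe, persistent hyperglycemia, as described in Section 6.1.4".
- Section 6.8.5 permits a sulfonylurea increase when the severe, persistent hyperglycemia criteria are met. It cites Section 8.3.3.7, which points back to Section 6.1.4.
- SAP Section 4.6.2.2 plans a rescue summary: "A summary statistic of initiation of rescue therapy in response to severe, persistent hyperglycemia will be provided by treatment".
- The Efficacy Analysis Set (EAS) drops data collected after rescue starts (Protocol Section 9.2, SAP Section 3).

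**The concern.** The cell is an operating instruction to sites, and it holds two thresholds. A site that reads HbA1c in mmol/mol would start rescue from about 8.0%; a site that reads it in percent would start from 8.5%. The trial recruits in North America and the EU, and the documents do not say in which unit sites receive HbA1c results.

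For a participant between the two thresholds with no FBG trigger, guidance conflicts on whether to start rescue. If no other circumstance in Section 6.8.4 applies, it also conflicts on whether the added drug is permitted at all. The number of rescues, and the data that leave the EAS, then depend partly on which half of the cell each site follows.

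**Working it through.** **Inputs.** Rescue pair: 8.5% and 64 mmol/mol (Protocol 6.1.4). Conversion anchors: 7.0% = 53 and 9.5% = 80 mmol/mol (Protocol 5.1, criterion 3).

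**Conversion from the protocol's own anchors.**

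- Slope = (80 − 53) / (9.5 − 7.0) = 27 / 2.5 = 10.8 mmol/mol per percentage point.
- 8.5% → 53 + 1.5 × 10.8 = 69.2 mmol/mol. The stated 64 is not reproduced.
- 64 mmol/mol → 7.0 + 11 / 10.8 = 8.02%.

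**Could rounding explain it?** Moving each anchor by ±0.5 mmol/mol gives 68.7 to 69.7 mmol/mol for 8.5%, and 7.97% to 8.06% for 64 mmol/mol. It cannot. As a cross-check only, take the standard linear relation mmol/mol = 10.929 × (% − 2.15) as an assumption. It returns 53.0 and 80.3 for the two anchors and 69.4 for 8.5%.

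**Values on which the two units disagree.**

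| mmol/mol | % (anchors) | Meets ≥64 mmol/mol | Meets ≥8.5% |
|---|---|---|---|
| 64 | 8.02 | yes | no |
| 65 | 8.11 | yes | no |
| 66 | 8.20 | yes | no |
| 67 | 8.30 | yes | no |
| 68 | 8.39 | yes | no |
| 69 | 8.48 (8.5 to one decimal) | yes | yes |

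**Is the fault isolated?** Dividing the FBG limits by 18.016 (assumed mg/dL per mmol/L for glucose) gives 270 → 14.99, 240 → 13.32 and 200 → 11.10 mmol/L. All agree with the printed 15.0, 13.3 and 11.1. Only the HbA1c pair fails.

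**How many participants could be affected?** The documents give no Week 32 mean or SD, so the inputs here are assumptions. With normal Week 32 HbA1c, the share from 8.02% to below 8.5% is:

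| SD | Mean 6.3% | Mean 6.9% | Mean 7.5% |
|---|---|---|---|
| 0.9 | 2.1% | 6.9% | 14.9% |
| 1.1 | 3.6% | 8.2% | 13.7% |
| 1.3 | 4.8% | 8.6% | 12.4% |

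In an arm of 125 that is 125 × 0.021 ≈ 3 to 125 × 0.149 ≈ 19 participants. Within these inputs it overstates rescues, because it ignores FBG-triggered rescue and investigator assessment. It is not a bound beyond them: a mean of 8.0% with SD 0.9 would put about 20% in the band.

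**Effect on the efficacy-estimand contrast.** This was simulated with 40,000 trials of 125 per arm. The SD (1.1) and true difference (−0.60) are those of Protocol Section 9.5. Only Weeks 32 and 40 were modelled, with one covariance matrix for both arms, and Week 40 was removed for participants at or above the threshold at Week 32. Standard errors when all of them are rescued:

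| Dulaglutide mean | Correlation | SE, 8.5% rule | SE, 8.02% rule | Rise |
|---|---|---|---|---|
| 6.9% | 0.6 | 0.1418 | 0.1454 | 2.5% |
| 6.9% | 0.8 | 0.1405 | 0.1426 | 1.5% |
| 6.9% | 0.9 | 0.1397 | 0.1408 | 0.8% |
| 7.5% | 0.6 | 0.1466 | 0.1547 | 5.5% |
| 7.5% | 0.8 | 0.1433 | 0.1480 | 3.3% |
| 7.5% | 0.9 | 0.1412 | 0.1437 | 1.8% |

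If half of them are rescued, the rise is 0.3% to 2.1%. The mean estimate stays at −0.600 to −0.601 in every case.

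**The case against.** The strongest reply accepts the conversion error and disputes its weight.

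- **The percent value is the natural reading.** It comes first, and 8.5% recurs as the HbA1c cut-point, as in the subgroup list ("baseline HbA1c (≤8.5%, >8.5%), and"), the stratification and the models, always in percent only. This stands. It points to the likely correction but does not help a site whose results arrive in mmol/mol.
- **Exposure is narrow.** Week 32 is the only scheduled HbA1c between Weeks 24 and 40, and FBG is a separate, correctly converted route. Rescue also passes through judgement: Section 6.1.4 says an added drug "may be medically indicated after investigator assessment", and Section 8.3.3.7 says "An additional therapeutic intervention should be considered in participants who develop severe, persistent hyperglycemia after randomization". Investigators are to be trained on the criteria, and that material may give one threshold. All of this limits the effect without correcting the cell.
- **No analysis rule uses the threshold.** The EAS and the rescue summary are driven by actual initiation of rescue, so both can be programmed without knowing which unit was meant. This is right. The link to the analyses runs only through what investigators do.
- **The simulation rests on assumed inputs and two visits**, not on the full planned repeated-measures model (MMRM). This is also right. It illustrates scale, and the finding does not depend on it.

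**Conclusion.** The concern holds. The two halves of the HbA1c rescue criterion differ by about 5 mmol/mol, or half a percentage point, by the protocol's own conversion. Rounding does not close the gap, and neither document corrects it. This part rests on no outside assumption.

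The consequence is inconsistent treatment guidance for participants at 64 to 68 mmol/mol after Week 24 who have no FBG trigger. If 8.5% was intended, acting on 64 mmol/mol starts rescue early and leaves nobody at or above 8.5% without it.

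No bias is shown in either primary analysis. The observed HbA1c that triggers rescue stays in the MMRM, and the Full Analysis Set keeps post-rescue data. Any loss of precision for the efficacy estimand is small: about 1% to 6% in the standard error as a ceiling within the assumed inputs. The share of participants in the band is unknown. The error should be fixed because it is an operative treatment threshold, not because it threatens the trial's conclusion.

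**What to change.** Change the cell in Protocol Section 6.1.4 to ≥8.5% (≥69 mmol/mol). If the sponsor confirms that the lower threshold was intended, it should read ≥8.0% (≥64 mmol/mol) instead. Send sites a clarification stating the single threshold in both units, and use the same pair in the investigator training that Section 6.1.4 already plans.

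The cost is a one-cell protocol correction, whatever ethics or regulatory notification that requires, and a site communication. The analyses and the sample size do not change.
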